### 18.4.3 Dose Escalation Rule and Choice of Cohort Size

Dose escalation will begin with 2 patients enrolled at the initial starting dose. The cohort size is 2, which means that 2 patients will be assigned to escalate to the next dose level, de-escalate to the prior dose level, or, stay at the current dose level.

On the completion of each cohort (i.e., 2 patients treated and assessed for DLT after 1-cycle), the posterior distributions of  $\theta(d)$  are summarized for each dose level by the probabilities of under-dosing, targeted toxicity, or excessive/unacceptable toxicity. These 3 probabilities are defined as:

$$\text{Under-dosing: } \theta_d \in (0, 0.20)$$

$$\text{Targeted Toxicity: } \theta_d \in [0.20, 0.35]$$

$$\text{Excessive or Unacceptable Toxicity: } \theta_d \in (0.35, 1]$$

The dose which maximizes the probability of targeted toxicity while controlling the probability of excessive or unacceptable toxicity to  $\leq 25\%$  will be recommended for the next cohort of 2 patients. The model has the flexibility for a larger cohort size if additional patient are available.

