### 2.4 Plans and Justification for Provisional Dose Levels

Overall, approximately 10 dose levels are planned. An initial increase of 100% for lower dose levels is foreseen, resulting in provisional dose levels of 30, 60 and 120  $\mu\text{g}/\text{kg}$ . Midstage escalation is somewhat more conservative to account for potential low-grade toxicity to become apparent, with dose level increases of 50%, 33% and 25%, resulting in doses of 180, 240 and 300  $\mu\text{g}/\text{kg}$ . Subsequent levels are determined by a fixed dose increase of 50  $\mu\text{g}/\text{kg}$  (i.e., 300, 350, 400, 450 and 500  $\mu\text{g}/\text{kg}$ ) as the highest dose level to be tested, if allowed by the mCRM with EWOC. The default dosing regimen is once every 3-week dosing. Clinical and pharmacokinetic (PK) data will be reviewed on an ongoing basis and may provide evidence to support interim dose levels. In addition, or as an alternative to decreasing doses to interim dose levels, the dosing interval may be extended (but not shortened), for example, to dosing every 4, 5 or 6 weeks instead of every 3 weeks. Once the dose interval is changed or an intermediate dose not predefined in the mCRM model is used, 3+3 design may be used for future dose escalation. One situation in which such approach may be advantageous is drug accumulation; implementation will need DESC approval (DESC, see [Section 4.6.1](#)) and may affect both ongoing patients as well as new cohorts. Similarly, it is at the discretion of the DESC to modify the dosing regimen that mandates omitting dosing of every n-th cycle, e.g. every 3rd cycle. Note: Scheduled visits will be kept,

except when C2 dosing is skipped; in that case C2D2-D5 would be omitted (respective assessment will not be done). This approach may be beneficial in balancing efficacy and adverse events. The cumulative dose of ADCT-502 in such a revised regimen can only be less than or equal to the cumulative dose of a dose-level that has been tested and found to be safe per mCRM.

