**Table 9: Planned Dose Levels for ADCT-502**

Dose Level	Dose of ADCT-502	Dose Level	Dose of ADCT-502
1	30 µg/kg	7	240 µg/kg
2	60 µg/kg	8	300 µg/kg
3	120 µg/kg	9	350 µg/kg
4	150 µg/kg	10	400 µg/kg
5	180 µg/kg	11	450 µg/kg
6	210 µg/kg	12	500 µg/kg

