### 18.4.2 Model and Priors

Dose escalation in this study will be conducted using the mCRM.

For each dose,  $d = 1, \dots, n$ , we model the binary outcome of non-DLT, or a DLT.

The log odds of a DLT are modeled as

$$\theta_d = \log\left(\frac{\pi_{DLT}}{1 - \pi_{DLT}}\right)$$

with a 2-parameter model

$$\theta_d = \alpha + \exp(\beta) \log(d_i / d^*)$$

where  $d^*$  is the reference dose, which is used to standardize the dose  $d_i$  and allows for the interpretation of  $\alpha$  as the odds of a DLT at  $d^*$ .  $\exp(\beta)$  is positive, ensuring a monotonically increasing dose-toxicity relationship.

[Neuenschwander, 2008](#) placed a bivariate lognormal prior on the two parameters and proposed eliciting information on the risk of DLT at two (2) or more doses to obtain prior means and variances. Several articles have examined the specification of priors. When there are no previous historical clinical data available, it is possible to use uninformative prior. For this purpose, the above model can be re-parametrized in terms of  $(\rho_0, \gamma)$ , where  $\rho_0$  is the probability of a DLT at the starting dose  $d_1$  and  $\gamma$  is the MTD, the dose expected to produce DLT at 0.3 probability in this study, with

$$\gamma = \exp(-\beta) * (\log(\theta_d) - \log(1 - \theta_d) - \alpha)$$

and placing the following independent prior distributions on the parameters.

$$\rho_0 \sim \text{Uniform}(0, 0.30)$$

$$\gamma \sim \text{Uniform}(d_1, d_n).$$

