### **18.4.3.1 Stopping Rules**

Patients will continue to be recruited into the study until 3 cohorts of patients are consecutively assigned to the same dose level, which will be identified as the MTD.

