**Scenario 3: True Probability of a DLT (with 0.02, 0.04, 0.06, 0.07, 0.08, 0.09, 0.105, 0.125, 0.165, 0.22, 0.3, 0.45)**

**Scenario 4: True Probability of a DLT (with 0.10, 0.125, 0.16, 0.19, 0.22, 0.25, 0.30, 0.37, 0.5, 0.6, 0.7, 0.8)**

**Scenario 5: True Probability of a DLT (with 0.13, 0.15, 0.17, 0.18, 0.19, 0.20, 0.21, 0.22, 0.24, 0.30, 0.36, 0.44)**

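### With cohorts of exactly 2, the printed mCRM stops a DLT-free trial at level 9 (350 µg/kg) and calls it the MTD; levels 10–12, and the true MTDs of Scenarios 3 and 5, are not reached

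*Protocol*

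**What the plan says.** Protocol Table 9 lists twelve levels from 30 to 500 µg/kg. Section 2.4 presents 500 µg/kg "as the highest dose level to be tested, if allowed by the mCRM with EWOC".

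Section 18.4.2 gives a two-parameter logistic model in log dose. The DLT probability at the starting dose has a uniform prior on 0 to 0.30, and the MTD has a uniform prior from the lowest to the highest dose. Section 18.4.3 sets cohorts of 2 and recommends "The dose which maximizes the probability of targeted toxicity while controlling the probability of excessive or unacceptable toxicity" to at most 25%; targeted toxicity is 0.20 to 0.35 and excessive toxicity is above 0.35. Section 18.4.1 rules out dose skipping. Under Section 18.4.3.1, recruitment runs "until 3 cohorts of patients are consecutively assigned to the same dose level, which will be identified as the MTD".

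Section 18.4.5 says that 1,000 trials were simulated per scenario. Among the five assumed curves, Scenario 3 puts the 0.30 rate at level 11 (450 µg/kg) and Scenario 5 puts it at level 10 (400 µg/kg).

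Sections 4.6 and 18.4.3 also allow, without requiring, larger cohorts and extra patients.

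**The concern.** A reader of Table 9 and Section 2.4 would expect only observed DLTs or overdose control to keep the trial below 500 µg/kg. A third mechanism can do so. The recommendation maximises the probability of the target interval, and the MTD prior has no mass above 500 µg/kg. Even with clean data, the rule can therefore prefer the current level by a small margin for long enough to trigger the three-cohort stop. That level is then recorded as the MTD although no toxicity has limited the dose.

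At stake are the meaning of the MTD label, which is the Part 1 primary objective in both the protocol and the SAP, and the value of Scenarios 3 and 5 as evidence that the design can find a high MTD.

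**Working it through.** **Inputs (protocol).**
- Doses from Table 9: 30, 60, 120, 150, 180, 210, 240, 300, 350, 400, 450, 500 µg/kg.
- Model and priors from 18.4.2: ρ0 ~ U(0, 0.30); γ ~ U(30, 500).
- Rule from 18.4.1, 18.4.3 and 18.4.3.1: as described above, with one level moved at a time.

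**Readings I had to adopt.** The γ formula in 18.4.2 does not match the model, so I used the stated meaning of the parameters: ρ0 is the DLT probability at 30 µg/kg, and γ is the dose with DLT probability 0.30. The symbol θ is defined as a log odds but given intervals on the 0–1 scale; I read those intervals as probabilities.

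**Formula.** logit p(d) = logit ρ0 + [logit 0.30 − logit ρ0] × [log d − log 30] / [log γ − log 30]. The reference dose cancels. With no DLTs the likelihood is ∏ (1 − p(d_j))^(n_j). The posterior was integrated over a 500 × 500 grid of (ρ0, γ).

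**The DLT-free path.** The levels assigned are 1, 2, 3, 4, 5, 6, 7, 8, 9, 9, 9. That is 11 cohorts × 2 = 22 patients. The decisive comparisons are:

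| After cohort at level 9 | Patients so far | P(target), level 9 | P(target), level 10 | P(excess), level 10 | Rule |
|---|---|---|---|---|---|
| first | 18 | 0.875 | 0.840 | 0.159 | stay |
| second | 20 | 0.888 | 0.874 | 0.124 | stay |

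The third cohort at level 9 triggers the stop. Only its data would reverse the order (0.895 at level 9 against 0.903 at level 10, on a 200 × 200 grid), and by then escalation has ended. Overdose control never excludes level 10, because both values are below 0.25.

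**Stability.** On grids from 160 × 160 to 2,500 × 2,500, the second comparison moves only from 0.893 against 0.876 to 0.887 against 0.873. If γ is uniform on log dose, the path is 1 to 8, 8, 9, 9, 9. That is 12 × 2 = 24 patients, with the same end level.

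**Scenarios, cohorts of 2.**
- Scenario 3: none of 4,000 simulated trials per setting went above level 9. Enumeration of outcome paths, with about 0.3% of probability unresolved, gave the same maximum. Level 11 was selected in 0%. Levels 8 and 9 took about 42% each.
- Scenario 5: level 10 was selected in 0% of 2,000 trials.

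The two misses differ in kind. In Scenario 3, every level up to 9 has a true rate of at most 0.165, which 18.4.3 classes as under-dosing. In Scenario 5, levels 6 to 9 have true rates of 0.20 to 0.24. These lie inside the target interval, so missing level 10 there is not under-dosing by the protocol's own definition.

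**Departures from cohorts of 2.**
- Cohorts of 3: the DLT-free path ends at level 10 (36 patients). Level 10 is selected in about 12% of Scenario 3 trials, with a mean size of about 34 against the roughly 30 patients planned.
- Three extra DLT-free patients, once: with the dose-uniform prior, adding them at any one of levels 4 to 9 opens level 10. With the log-uniform prior, only adding them at level 9 does.
- Level 11 was still never selected in Scenario 3 with cohorts of 3 or 4, or with three extra patients per cohort from level 2 (2,000 trials each).

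There is no printed figure to reproduce, because the sponsor's simulation results are in figures not shown.

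**The case against.** A reader might infer that the plan always stops at an under-dose if the drug is as well tolerated as Scenario 3 assumes, and that all Part 2 testing would then run at that dose. The documents do not support this:

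- Section 18.4.3 allows larger cohorts. Section 4.6 allows up to three extra breast cancer patients per cohort from 60 µg/kg, and further patients after a response or for PK or PD. These routes can open level 10, whose true rate in Scenario 3 (0.22) is in the target interval.
- The steering committee confirms each dose and may modify the schedule (4.6, 4.6.1). Intermediate doses, with 3+3 afterwards, are permitted (2.4), and more than one expansion dose may be chosen (4.6).
- Section 2.4 calls the levels provisional and makes 500 µg/kg conditional on the model.
- The appendix text prints only assumed curves. It claims no success rate for Scenario 3, and the figures may already show low selection at the upper levels.

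The margin is also small (0.035, then 0.014), and a model linear in dose would reach level 10 even with cohorts of 2. The error is towards lower doses in a first-in-human study, and the SAP (3.3) records that Part 2 was not performed.

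All of this limits the consequences. It does not remove the core point. The extra patients are optional and unquantified, committee discretion lies outside the model, and the printed model is in log dose. As printed, the rule gives an MTD label to a DLT-free trial.

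**Conclusion.** The point holds for the rule as printed, with cohorts of exactly 2 and dose entering on the log scale. A trial with no DLT stops at 350 µg/kg after 22 patients (24 with γ uniform on log dose) and labels that level the MTD. Levels 10–12 are not reached, and the true MTDs of two of the five scenarios are selected in 0% of simulated trials. The cause is the combination of an MTD prior bounded at the top dose, the maximisation criterion and the three-cohort stop. Overdose control is not the cause.

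The result rests on my reading of the inconsistent γ and θ notation in 18.4.2–18.4.3. It says nothing about the settings the sponsor actually simulated, which cannot be checked. It does not show that every trial would end in an under-dose or that Part 2 would be tied to level 9. This should be fixed, but it creates no excess-toxicity risk.

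**What to change.** Reconcile Appendix 18.4 with Table 9, Section 2.4 and Scenarios 3 and 5:

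1. State the highest level that the printed rule can recommend with cohorts of 2, and how optional extra patients change this.
2. Report the selection percentage for every level in all five scenarios, under the settings actually used (cohort size, extra patients, dose scale, prior).
3. If those settings differ from the printed model, prior or rule, correct the printed text, including the γ formula and the double use of θ.
4. When the three-cohort stop applies while the next level still satisfies overdose control and few or no DLTs have been seen, report the level as the highest evaluated, with the MTD not reached. State in advance what counts as few. Section 4.6 already provides for an expansion dose when the MTD is not reached, so this changes only the label. Carry the same wording into the study report.

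The cost is wording, plus tabulating the existing simulations or re-running them.

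Widening the upper bound of the MTD prior is not part of this fix. As an illustration, with cohorts of 2 a bound of 600 takes the DLT-free path to level 11 and 750 takes it to level 12. Over-toxic selection in Scenario 4 then rises from about 16% to 29–35%. That trade-off is for the sponsor to weigh.

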### **18.4.3.1 Stopping Rules**

Patients will continue to be recruited into the study until 3 cohorts of patients are consecutively assigned to the same dose level, which will be identified as the MTD.

### **18.4.4 Interim Monitoring**

The study will be continuously monitored for safety and for success in identifying the MTD. If dose escalation is not stopped for either safety or success in identifying the MTD, it will continue to enroll to the maximum sample size.

[figure not shown]
#### **18.4.4.1 Safety Monitoring**

[figure not shown]
The lowest dose (the initial starting dose) will be considered unsafe if the probability of excessive or unacceptable toxicity is  $> 25\%$ . The trial will stop, and no MTD found, if the lowest dose is considered unsafe (hence all doses are considered unsafe).

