#### **4.6 Description of Dose Escalation Process**

Each cohort will consist of 2 patients. There will be a 24-hour observation before enrolling the second patient at Dose Level 1. The DLT observation period at each dose level is 1 cycle (3 weeks), after which it will be determined whether to escalate to the next dose level, stay at the current dose level, or de-escalate to the previous dose level for the next cohort.

There will be no de-escalation from Dose Level 1. Intrapatient dose escalation is not permitted.

Dose escalation is not permitted unless two or more patients have complete DLT information through the first cycle in any given dose level. Dose escalation will be determined by using a mCRM with a target DLT rate of 30% and an equivalence interval of 20% to 35%, and with dose escalation-with-overdose-control (EWOC) and no dose skipping.

The mCRM will be implemented in Part 1 under the oversight of a Dose Escalation Steering Committee (DESC). The DESC will confirm each escalating dose level after reviewing all available safety data. PK data from patients in that dose level and prior dose levels may also inform decision making. The DESC may halt dose escalation prior to determining the MTD based on emerging PK, PD, toxicity, or response data.

Additional patients may be included at any dose level to further assess the safety and tolerability if at least 1 patient in the study has achieved a partial response or better, or if further evaluation of PK or PD data is deemed necessary by the DESC to determine the RDE.

Furthermore, to better understand the potential efficacy of ADCT-502 in an indication approved for treatment with HER2 targeted antibodies, up to 3 additional breast cancer patients who have previously been treated with an approved HER2 targeted therapy may be enrolled per cohort at given dose levels  $\geq 60 \mu\text{g/kg}$  determined by the mCRM model to be safe.

Dose escalation will be stopped after the mCRM has assigned 3 cohorts consecutively to the same dose level.

If the MTD is not reached, the recommended dose(s) and schedule(s) for expansion (RDE) will be determined.

Once the Part 2 RDE(s) is/are determined, patients receiving lower or higher dose levels of ADCT-502 enrolled in part 1 may be offered continued treatment at the RDE(s).

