#### 4.6.1 Safety Oversight by the Dose Escalation Steering Committee

A DESC comprised of ADC Therapeutics and the investigators will review patient safety on an ongoing basis during Part 1 to determine if the dose escalation schedule prescribed by the mCRM warrants modification. In addition to safety observations, PK and/or PD data may also inform DESC decision making. Intermediate doses or extended dosing intervals may be assigned after agreement between ADC Therapeutics and the investigators. The DESC will continue to provide oversight during Part 2. No formal Data Safety Monitoring Board (DSMB) will be used.

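### The model-based stop for a toxic starting dose can never fire, because the prior caps the level 1 DLT probability at 0.30 and the rule looks for values above 0.35

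*Protocol*

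**What the plan says.** Three parts of Protocol Appendix 18.4 bear on this.

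- **Section 18.4.2 (model and priors).** A two-parameter logistic model in log dose is re-expressed through rho0 and gamma. The text says that rho0 "is the probability of a DLT at the starting dose". Gamma is the MTD, the dose with a DLT probability of 0.30. Rho0 is uniform on 0 to 0.30, and gamma is independently uniform from the lowest to the highest dose level, 30 to 500 µg/kg in Table 9.
- **Section 18.4.3 (escalation rule).** Excessive toxicity is the interval above 0.35. The next dose is the one with the largest posterior probability of the target interval, 0.20 to 0.35, among doses whose probability of excessive toxicity is at most 25%.
- **Section 18.4.4.1 (safety monitoring).** The starting dose is unsafe if its probability of excessive toxicity is above 25%. Then: "The trial will stop, and no MTD found, if the lowest dose is considered unsafe (hence all doses are considered unsafe".

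The only other model-based end to escalation is in section 18.4.3.1: three consecutive cohorts at one level make that level the MTD. Section 4.6 allows no de-escalation from level 1. Outside the model, section 4.6 provides that "The DESC will confirm each escalating dose level after reviewing all available safety data", and section 4.6.1 has the committee review safety "to determine if the dose escalation schedule prescribed by the mCRM warrants modification".

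**The concern.** The stop rule asks whether the level 1 DLT probability is likely to exceed 0.35. The prior has already ruled out any value above 0.30. If so, the rule is inert, and so is the 25% overdose limit at level 1. This is a first-in-human trial, and this is the only statistical rule that covers the case where every dose is too toxic. Without it, the algorithm can only finish by naming an MTD, even when the starting dose is itself above the acceptable range. The DESC would also be reading a model output that can never flag level 1.

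**Working it through.** The protocol states no operating figure for this rule, and the operating-characteristic plots are not in the text available, so there is no stated result to reproduce.

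**Step 1: the exact argument.** The prior density of rho0 is zero above 0.30 (section 18.4.2). The posterior is proportional to prior times likelihood, so it is also zero there. Hence P(level 1 rate > 0.35 | data) = 0 for every data set, against the > 0.25 required by section 18.4.4.1.

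Two ambiguities in the appendix do not change this:
- Section 18.4.2 defines theta as log odds, while section 18.4.3 uses it as a probability. Read as log odds, 0.35 is a probability of 1/(1 + exp(−0.35)) = 0.587, still above 0.30.
- Gamma may be meant as uniform on dose or on log dose. Neither affects the cap on rho0.

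**Step 2: how level 1 behaves.** With x DLTs in x patients at level 1 only, the posterior of rho0 is proportional to rho0^x on (0, 0.30). Its mean is 0.30(x + 1)/(x + 2).
- 2/2 DLTs: 0.30 × 3/4 = 0.225
- 6/6 DLTs: 0.30 × 7/8 = 0.262
- 20/20 DLTs: 0.30 × 21/22 = 0.286

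Even 20 DLTs in 20 patients leave level 1 estimated below the 0.30 target. A numerical posterior gives a level 1 excess probability of 0.000 in all these cases.

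**Step 3: what the model recommends after the first cohort.** After re-parametrisation the reference dose cancels:

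logit p(d) = logit(rho0) + [logit(0.30) − logit(rho0)] × log(d/30) / log(gamma/30)

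The posterior was computed on a grid, with gamma uniform either on dose or on log dose.

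| DLTs at 30 µg/kg | P(excess at 30) | P(excess at 60), dose scale | P(excess at 60), log scale | Next dose, no skipping |
|---|---|---|---|---|
| 0/2 | 0 | 4.5% | 18.7% | 60 µg/kg |
| 1/2 | 0 | 3.6% | 15.5% | 60 µg/kg |
| 2/2 | 0 | 3.0% | 13.2% | 60 µg/kg |

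After 2/2 DLTs, P(target) at 30 µg/kg is 1 − (0.20/0.30)^3 = 0.704. At 60 µg/kg it is 0.837 (dose scale) or 0.786 (log scale), so the rule prefers 60.

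The apparent risk at 60 µg/kg falls as DLTs accumulate at 30. DLTs at level 1 push rho0 towards its ceiling of 0.30. Because the curve must still pass through 0.30 at a gamma no lower than 30 µg/kg, it flattens.

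The overdose limit can act above level 1. On the dose scale, after 0/2 at 30 and 2/2 at 60, P(excess at 60) is 0.395 and only level 1 remains admissible.

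**Step 4: illustration with a toxic start.** The true rates here are assumptions, not protocol figures, and no DESC intervention is modelled. Cohorts of 2, 2,000 simulated trials per case.

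| Assumed true rates, levels 1 to 4 | Gamma scale | Safety stops | Level 1 named MTD | Mean patients | Mean DLTs |
|---|---|---|---|---|---|
| 0.50, 0.60, 0.70, 0.75, rising | dose | 0% | 49% | about 14 | about 8 |
| same | log | 0% | 61% | about 10 | 5.6 |
| 0.40, 0.50, 0.60, 0.65, rising | dose | 0% | 34% | 14.8 | 7.4 |
| same | log | 0% | 44% | 10.2 | 4.6 |

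The remaining trials named a higher level. A 60-patient cap, set for the simulation because the protocol gives no maximum, was never reached.

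**Step 5: could the protocol's simulations have shown this?** The level 1 rates in scenarios 1 to 5 (section 18.4.5.1) are 0.10, 0.05, 0.02, 0.10 and 0.13. All lie well below 0.35, so a missing stop at level 1 would not be visible in any of them.

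**The case against.** The strongest reply is that the model does not run the trial. The DESC must confirm each escalation, may halt it before an MTD is found because of toxicity, and may change the schedule. An escalation after two DLTs in two patients is therefore a recommendation that would be reviewed. This stands: the simulated patient and DLT counts are not expected harm, and the true rates behind them are assumed. Section 2.3 describes a starting dose with a safety factor, and nothing visible suggests that rates of 40% or 50% were likely. But it does not restore the rule. Section 18.4.4.1 promises a statistical stop that does not exist, and the schedule put before the committee would lean towards escalation.

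A second reply is that section 18.4.2 introduces this prior only as a possibility, and its notation is loose, so the program actually used may differ. That is possible, and the exact zero applies to the prior as written. No other prior is given, however. If the program used one, the protocol misdescribes the design and still needs correction.

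Third, SAP section 3.3 records early termination without Part 2, and SAP section 4.8.1 only lists DLTs, so no planned analysis depends on this rule. That is true and limits the consequence for reporting. It does not alter the error in the Part 1 design.

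**Conclusion.** The concern holds. Under the prior as written, the posterior probability of excessive toxicity at level 1 is exactly 0 for any data, so the stop in section 18.4.4.1 and the 25% limit at level 1 can never act. This part rests on no assumption beyond the stated prior. The recommendation of 60 µg/kg after 0, 1 or 2 DLTs in the first two patients holds for both readings of gamma's scale. The simulated selection rates and trial sizes are illustrations only: they depend on the assumed true rates, on gamma's scale and on the absence of DESC action. The contradiction has to be removed from a first-in-human design, although the committee's authority means that patients were not left without protection.

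**What to change.** What the contradiction itself requires:

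1. Reconcile sections 18.4.2, 18.4.3 and 18.4.4.1. The prior must allow a level 1 DLT probability above 0.35 and, jointly, an MTD below the lowest dose. Widening rho0 alone does not work: with rho0 = 0.50 and gamma = 240 µg/kg the slope is [logit(0.30) − logit(0.50)]/log(240/30) = −0.847/2.079 = −0.41, which contradicts the model's positive slope.
2. Add at least one scenario with a toxic starting dose to section 18.4.5.1, and report the probability of stopping.

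Useful in the same revision:

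3. State whether gamma is uniform on dose or on log dose, and use one meaning for theta.
4. Tabulate which DLT counts at level 1 trigger the stop.
5. Report, for every scenario, the false-stop rate and how often a dose with a true rate above 0.35 is selected.

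The cost is appendix text and a re-run of the simulations. The price in performance is a false-stop probability that is no longer zero. A looser prior may also enlarge Part 1 or raise selection of overly toxic doses.

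Calibration matters. As a simplified illustration, take a Uniform(0, U) prior on the level 1 rate alone, with no dose model. P(rate > 0.35) after 0/2, 1/2 and 2/2 DLTs is:
- U = 0.40: 0.075, 0.200, 0.330
- U = 0.60: 0.225, 0.565, 0.802
- U = 1.0: 0.275, 0.718, 0.957

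Against the 25% limit, the first would stop only at 2/2, the second from 1/2, and the third even at 0/2. The choice of prior is left to the sponsor's calibration.
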